14.2 Reporting of Adverse Events

The Medtronic Clinical Research Department, in conjunction with the Medtronic Regulatory Affairs Department, in Northridge, California will monitor and manage adverse event reporting for the study.

A complete description of the event including treatment and interventions provided by medical professionals will be included on the AE eCRF. It is expected that the investigator will provide the sponsor with the necessary medical records to support the adverse event.

Throughout the course of the study, Investigational Center staff will make all efforts to remain alert to possible reportable adverse events or untoward findings. Reports of adverse events will be requested from subjects/parents/caregivers at each visit and adverse event eCRFs will be completed as required. Investigational Center staff will assess the intensity of each adverse event and its relationship to study procedures or devices.

Adverse events that are assessed to have a relationship to a study procedure or study device will be analyzed by the Human Factors group at Medtronic Diabetes to determine whether or not there is a connection to mis-use of the device(s) or user error.

Events that are moderate and severe in intensity, all SAE, SADE and UADE that have not resolved at the time of the subject's discontinuation or completion of the study will be followed until the medical outcome is determined or until no further change in the condition is expected. All adverse events that have not resolved will have a final status of 'ongoing'.

Adverse Events reported to sponsor:

The Investigator or designee will report all adverse events to the sponsor:

- Adverse Events not related to the study device or study procedure
- Adverse Events related to the study device
- Adverse Events related to study procedures
- UADE (Unanticipated Adverse Device Effect)
- All SAE (Serious Adverse Events)
- Severe Hypoglycemia
- DKA (Diabetic Ketoacidosis)

A pre-existing medical condition will only be documented as an adverse event if the condition worsens during the course of the subject's participation in the study. Non-serious Adverse events should be entered on the appropriate Electronic Case Report Form (eCRF) within 14 days of subject report to the site. For serious adverse events, reporting is required to sponsor within 24 hours of site awareness.

14.3 Review of Severe Hypoglycemia and DKA.

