Severe hypoglycemia, and DKA will be adjudicated by the Clinical events committee (CEC) comprised of external physicians. The adjudication will include device relatedness and whether the event was considered to be serious or not. The CEC may use Carelink reports, medical records and information on CRF to make determination.

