The relatedness of the event to the study device or procedures will be determined for each adverse event. Subjects participating in this study have type 1 diabetes and it is expected that due to the disease subjects will have adverse events that are part of their disease. It is expected that the investigator will assess all events to determine if the event was related to the disease or if the event was related to the device or study procedure. An adverse event is not automatically related to the study device or procedure simply because the subject is wearing the device and participating in the study. The event should be reviewed to determine if the device or study procedure could have possibly caused the event and therefore is related to the study device or procedure.

The investigator will review all elements surrounding the event to properly determine relatedness – this would include the subjects/parents/caregivers description of the event, study device downloads and medical records (if applicable) from the treating facility. These records will be made available to the

sponsor and the Clinical Events Committee at the request of the sponsor. The following definitions should be considered when determining the relationship of the event to the device or study procedure:

Definite – clearly related to the device or procedure

Probable – likely related to the device or procedure

Possible – may be related to the device or procedure

Unlikely – doubtfully related to the device or procedure

Not Related – clearly not related to the device or procedure

If the investigator determines the event meets the definition of definite, probable or possible the event should be considered related and the Yes box on the AE eCRF would be checked for the question related to. If the investigator determines the event meets the definition of unlikely, not related or unknown the event should be considered unrelated and the NO box would be checked on the AE eCRF for the question was the event related to.

14.6 Event Intensity (severity):

Mild: Transient, needing no special treatment, and/or does not interfere with the subject's daily activity.

Moderate: Low level of inconvenience or concern to the subject and may interfere with daily activities, but is usually improved by simple therapeutic remedy.

Severe*: Interrupts a subject's daily activity and typically requires intervening treatment.

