14.7 Clinical Events Committee

A clinical events committee consisting of external physicians with an expertise in Endocrinology and the management of Type 1 diabetes including CGM will be convened. The CEC will review all reports of:

- Diabetic Ketoacidosis
- Severe Hypoglycemia
- Serious Adverse Event
- Serious Adverse Device Effect
- Unanticipated Adverse Device Effect

The CEC will assess these events to determine agreement or disagreement with the investigator determination of the event. The investigator will be notified of any disagreement in assessment of an event by the CEC.

15. Administrative Considerations

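### Adverse events of unknown relatedness are coded as unrelated, which can only lower the device-related count and keeps them out of the human-factors review

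*Protocol*

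**What the plan says.** Protocol Section 14.5 asks the investigator to judge every adverse event and defines five answers: definite, probable, possible, unlikely and not related. These are reduced to a Yes/No answer. On the positive side: "definite, probable or possible the event should be considered related and the Yes box on the AE eCRF would be checked". On the negative side, the rule reads: "unlikely, not related or unknown the event should be considered unrelated". The form then carries a No for such an event. Unknown appears only in this second rule and has no definition.

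Two other parts of the protocol bear on such events.

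- Section 14.2 sets the entry condition for human-factors review: "Adverse events that are assessed to have a relationship to a study procedure or study device will be analyzed by the Human Factors group". Its purpose is "to determine whether or not there is a connection to mis-use of the device(s) or user error".
- Section 14.7 sets out the scope of the clinical events committee (CEC), opening with "The CEC will review all reports of". The list is DKA, severe hypoglycemia, serious adverse events, serious adverse device effects and unanticipated adverse device effects. For severe hypoglycemia and DKA, Section 14.3 adds: "The adjudication will include device relatedness and whether the event was considered to be serious or not".

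Protocol Section 6.4 and SAP Section 3.1.6 list the safety summaries, which include an Adverse Device Event line. Neither has a visible rule for events of unknown relatedness.

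**The concern.** Unlikely and not related are judgements that the device or procedure probably or clearly played no part. Unknown is the absence of a judgement. Putting all three in the same box records missing information as a negative finding.

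Two things are at stake in a single-arm device study. First, the count of device-related events may be too low, and the rule gives no way for it to be too high. Second, the human-factors review exists to detect misuse and user error, and Section 14.4 treats use error as a form of adverse device effect. An event of undetermined cause may be a use error, yet it does not meet the condition for that review.

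Undetermined cause is foreseeable here. Section 10.1 warns that the pump cannot detect a leaking set or insulin that has lost potency. Section 14.1.5 says the suspend feature may activate when glucose is not low. Either could contribute to a hyperglycemic event whose origin is hard to establish afterwards.

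**Working it through.** The point concerns a classification rule. The plan states no figure to reproduce, so the check traces an unknown event through the documents and then works out the direction of the error.

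**Step 1: where an unknown event goes**

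| Stage | Source | Event marked Yes | Non-serious event of unknown relatedness |
|---|---|---|---|
| eCRF answer | Protocol 14.5 | Yes | No |
| Reported to sponsor | Protocol 14.2 | Yes | Yes |
| All-event summaries | Protocol 6.4, SAP 3.1.6 | Included | Included |
| Adverse Device Event line | Protocol 6.4, SAP 3.1.6 | Included if related to the device | Not included |
| Human-factors review | Protocol 14.2 | Yes | No |
| CEC review | Protocol 14.3, 14.7 | If on the CEC list | Only if DKA or severe hypoglycemia |

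One assumption enters here. The summaries use the term Adverse Device Event, while Section 14.4 defines Adverse Device Effect. I take the line to be filled from the eCRF relatedness answer, since no other source is described.

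**Step 2: direction and bounds**

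Let R be the events marked Yes, N those judged unlikely or not related, U those of unknown relatedness, and q the fraction of U that is truly related. Take R and N as correctly judged.

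- Reported related count = R
- True related count = R + U × q
- Shortfall = (R + U × q) − R = U × q

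Since q lies between 0 and 1, the shortfall lies between 0 and U. It is never negative, so the rule cannot inflate the count. The documents give neither U nor q.

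**Step 3: whether the data could repair this later**

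With only Yes and No recorded, the database holds R and the sum N + U. The useful upper bound, R + U, needs U alone. The only bound recoverable from Yes/No data is R + N + U, which is all adverse events and so tells the reader nothing. A sensitivity count therefore depends on recording U separately when the form is completed.

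**Step 4: which events are exposed**

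Severe hyperglycemia is a named safety endpoint in the Protocol Synopsis but is not on the Section 14.7 list. Unless it is also serious, an unknown case gets neither CEC nor human-factors review. Serious events of unknown relatedness do reach the CEC. However, Section 14.7 says only that the investigator is told of a disagreement. It does not say that the eCRF answer changes or that human-factors review follows.

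**The case against.** The strongest reply is that Section 14.5 already sets a low bar for Yes. Possible counts as related, and the investigator is told to ask whether the device or procedure could have caused the event, using the family's account, device downloads and medical records. Most uncertain events with a plausible device role should therefore be coded possible, leaving unknown as a small residual class. This stands, and it limits the likely size of the problem.

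Other safeguards also stand. Every adverse event goes to the sponsor and into the summaries. The lines for infusion set, pump use, sensor use and severe hyperglycemia are not said to depend on relatedness. Sensor-site and infusion-set reactions are listed device risks, so they are poor candidates for unknown cause. Under Section 13, device deficiencies, including use errors, go to the Help Line, and sites review the calls for adverse events. The safety analysis is descriptive apart from confidence intervals and limits, and the limits for DKA and severe hypoglycemia are not restricted to related events.

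A reader might infer a large undercount. Suppose, for example, that 20% of events were coded related and a further 5% to 20% unknown. The related share could then be as high as 20% + 5% = 25% to 20% + 20% = 40%. Neither percentage is in the documents, and both results need every unknown event to be truly related (q = 1). They do not support a figure of this kind.

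What the reply does not remove is the explicit coding of an undefined category as No, the loss of the distinction once coded, and the exclusion from human-factors review.

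**Conclusion.** The point holds as a defect of classification with a known direction and an unknown size. The Adverse Device Event count, and any count of procedure-related events, can be too low by anything from 0 to U. A reader might go further and say the rule is shown to understate device-related harm. It is not: there is a shortfall only if at least one unknown event is truly related, and the documents do not show that.

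The consequence is confined mainly to non-serious events outside CEC review. The A1C analysis, the all-event summaries and the DKA and severe hypoglycemia limits do not use this answer. The point merits a correction but does not threaten the trial's main conclusion.

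Two limits apply. The eCRF itself is not among the documents, so the Yes/No structure is taken from Section 14.5. Parts of the SAP are redacted, so the absence of a rule for unknown relatedness is established only for the visible text.

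**What to change.** 1. In Protocol Section 14.5, remove unknown from the list treated as unrelated, and define it.
2. Add unknown as a separate response to the relatedness questions on the adverse event eCRF.
3. In Protocol Section 6.4 and SAP Section 3.1.6, report device-related and procedure-related events twice, excluding unknown (R) and including unknown as related (R + U), with U on its own line.
4. In Protocol Section 14.2, extend the human-factors review to events of unknown relatedness.

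Reporting both counts is preferable to making R + U the only headline figure. Counting every unknown event as related would replace one arbitrary default with its opposite, and Section 14.5 itself cautions against assuming relatedness merely because the device is worn.

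The cost is a short protocol and SAP edit, one added eCRF response option with its completion guidance, extra table lines, and a few more events for human-factors review. The upper count may look less favourable than the single count now planned.

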14.7 Clinical Events Committee

A clinical events committee consisting of external physicians with an expertise in Endocrinology and the management of Type 1 diabetes including CGM will be convened. The CEC will review all reports of:

- Diabetic Ketoacidosis
- Severe Hypoglycemia
- Serious Adverse Event
- Serious Adverse Device Effect
- Unanticipated Adverse Device Effect

The CEC will assess these events to determine agreement or disagreement with the investigator determination of the event. The investigator will be notified of any disagreement in assessment of an event by the CEC.

15. Administrative Considerations

15.1 Document Storage and Retention

The Sponsor and Investigator will retain all records and documents pertaining to this study. They will be available for inspection by the appropriate regulatory agencies. In addition, the Investigator will retain the source documents from which the information entered on the eCRF was derived. These records are to be retained in a secure storage facility maintained by the Investigational Center until 2 years after approval of the above-listed study devices or termination of the study, whichever is longer. The Investigator should not dispose of these records without the approval of the Sponsor.

15.2 *Data Handling*

All data required for analysis will be captured on electronic Case Report Forms (eCRFs) using Oracle Clinical's 21 CFR Part 11 compliant Remote Data Capture (RDC) module. Original eCRFs will not be used as source data and supporting documentation will be required. Electronic device data will be collected from the study pump using Medtronic CareLink Clinical, which is 21 CFR Part 11 compliant.

The Investigator will ensure that all eCRFs are completed promptly, completely, and accurately. Information on case report forms must conform to the information in the source documents. Medtronic will provide detailed instructions to assist with CRF completion. In the event of data discrepancies, Investigational Centers will be asked to resolve queries electronically in the RDC system; otherwise, irresolvable data-related issues will be routed to the Sponsor for review and final disposition. An audit trail is maintained in Oracle Clinical to capture any corrections or changes of the eCRFs. System backups for data stored in the Oracle Clinical system will be consistent with Medtronic standard procedures.

Medtronic will only consider eCRFs to be complete when all discrepancies between source data and eCRF have been resolved and eCRF content has been reviewed by a Study Monitor. In addition, specific eCRFs must also be reviewed and electronically signed by the Investigator, indicating his/her agreement with the accuracy of all recorded data. It is expected that the Investigator and his/her staff will cooperate with the monitoring team and provide any missing data in a timely manner.

15.3 Data Preparation

Prior to data extraction, all collected data will undergo a final verification by Data Management. Documentation of this verification will be maintained in the sponsor study files. Upon the completion of the verification, data will be extracted and transferred to the appropriate personnel for analysis.

15.4 Training of Clinical Staff

Training of the Investigational Center staff on the conduct of the study and system being studied will be initiated before the protocol is implemented. All participating physicians and coordinators will be familiarized with the system. Specific Investigational Center staff will be trained on each of the system's components. Training will contain both lecture and hands-on experience.

15.5 Study Binders

A Regulatory Binder and an Investigator/Coordinator Manual will be provided by the Sponsor to be maintained by Investigational Center staff. At a minimum, each Regulatory Binder will include:

- Study Contact Sheet
- Clinical Study Agreement(s)
- Signed/dated CV of Investigator(s)
- IRB Correspondence
- IRB-approved Protocol(s) and Informed Consent Form(s), including all amendments
- Clinical Bulletins- A brief official update or summary of current study news on a matter of immediate interest and high importance to Investigational Center surrounding the study protocol.
- Site Visit Sign-In Log
- Study Correspondence
- Site Signature and Study Delegation Log
- Training Records
- Sound Bites

At a minimum, the Investigator/Coordinator Manual will include:

- Sample Coordinator Worksheets
- User Guide(s), Instructions for Use, and/or User Manual as applicable
- Quick Reference Guide
- Training materials

1 OVERVIEW

1.1 Purpose

The Clinical BP (Biostatistical Plan) for the CEP 287 (Multi-Center, Prospective, Observational Study of the TS (Threshold Suspend) Feature with a Sensor-Augmented Pump System in Pediatric Patients with Type 1 Diabetes) study [REDACTED]

[REDACTED]

[REDACTED]

1.2 Scope

The contents of this Biostatistical Plan, written for the the CEP 287 (Multi-Center, Prospective, Observational Study of the TS (Threshold Suspend) Feature with a Sensor-Augmented Pump System in Pediatric Patients with Type 1 Diabetes), apply to the statistical analysis provided by Medtronic Diabetes Biostatistics.

1.3 History

[REDACTED]

2.1 Study Protocol

CEP287

2.2 CRF Development

Location of CRF: RAD

2.3 Statistical Analysis Plan

2.4 Statistical Analysis

2.4.1 Actual Randomization Sequence

N/A

2.4.2 Data Extraction, Preparation, and Validation

2.4.3 Statistical Programming

2.4.3.1 Validation

2.4.3.2 Programming code

2.4.4 Output and Final Report

2.4.5 Change from SAP

3 Appendix A

3.1 CLINICAL STATISTICAL ANALYSIS PLAN

3.1.1 Synopsis of Study

This study is a longitudinal, multi-center trial that aims to observe the Threshold Suspend (TS) feature with a sensor-augmented insulin pump in patients 2–15 years with Type 1 diabetes. The study will measure the change in A1C from baseline over a period of one year while subjects are wearing the study pump.

The study objective is to demonstrate that home use of Threshold Suspend (TS) is not associated with glycemic deterioration in pediatric patients with type 1 diabetes, as measured by change in A1C.

Up to 300 subjects will be enrolled so that there will be 200 subjects who are eligible to participate in the study.

Up to 20 Investigational centers will be selected across the United States. Selection is based on each Investigator's experience and qualifications, availability of sufficient resources to carry out the required study procedures and the investigator's ability to recruit subjects into the study.

3.1.2 General Statistical Considerations

3.1.2.1 Sample Size, if applicable

3.1.2.1.1 Sample Size for Primary Endpoint

The overall mean change in A1C from baseline to the end of study will be estimated and compared by a non-inferiority test with an A1C margin of 0.4% and a significance level of 0.025 (one-sided). The null hypothesis will be rejected if the one-sided 97.5% upper confidence limit of the mean change in A1C is less than 0.4%

The hypothesis is mathematically expressed as:

Ho: $\mu \geq 0.4\%$

Ha: $\mu < 0.4\%$

Where 0.4% is the pre-specified non-inferiority margin, μ is the mean of change in A1C (%).

Assuming the mean of change in A1C from baseline to the 12-month follow-up visit is zero, the standard deviation of change in A1C is 1%, SAS power and sample size calculator shows that a total of 100 subjects will provide over 95% power to detect the non-inferiority with a margin of 0.4% and with one-sided type I error of 0.025.

3.1.2.1.2 Overall Consideration

The above calculations suggest a sample size of 100 subjects who complete the study. For the drop-out rate, a conservative estimate of 20% is adopted (based on STAR3, IDE G060159, the percentage of subjects not completing study in the SAP group is 9.3%); assume 65% of subjects would wear the system most of the time. Then a total of 193 subjects needs to be recruited. In general, a number of 200 will be eligible to participate in the study, with up to 300 subjects enrolled

3.1.2.2 Analysis Datasets, if applicable

Intention to Treat (ITT) Population

The Intention to Treat (ITT) population will include all enrolled subjects.

Completed Case (CC) Population

The Completed Cases (CC) population is all subjects who complete the trial.

Efficacy Population

The primary analysis will be performed on the CC population. Sensitivity analysis will be performed in the ITT population with multiple imputations.

Safety Population

The safety population will be the ITT population (include all enrolled subjects).

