3.2. Study Hypothesis

Change in A1C is defined as A1C measured at the end of 12-month study period minus A1C measured at the baseline visit. The hypothesis is mathematically expressed as:

$$\begin{aligned} H_0: \mu &\geq 0.4\% \\ H_a: \mu &< 0.4\% \end{aligned}$$

Where 0.4% is the pre-specified non-inferiority margin, μ is the mean of change in A1C (%).

4. Study Design

This study is a longitudinal, multi-center trial that aims to observe the Threshold Suspend (TS) feature with a sensor-augmented insulin pump in patients 7–15 years with Type 1 diabetes. The study will measure the change in A1C from baseline over a period of one year while subjects are wearing the study pump.

5. Study Population

5.1 Number of Subjects and Study Population:

Up to 300 subjects will be enrolled so that there will be 200 subjects who are eligible to participate in the study.

Up to 20 Investigational centers will be selected across the United States. Selection is based on each Investigator's experience and qualifications, availability of sufficient resources to carry out the required study procedures and the investigator's ability to recruit subjects into the study.

Subjects will be grouped by baseline demographics: Baseline A1C, age, ethnicity, body mass index (BMI), gender and duration of diabetes and hypoglycemic awareness. Sponsor will oversee distribution of subjects across study sites.

- Baseline A1C
 - A1C less than 7.0% (Minimum N=50)
 - A1C between 7.0% to 9.0% (Minimum N=50)
 - A1C greater than 9.0% (Minimum N=50)
- Race
 - American Indian/Alaska Native
 - Black/African-American
 - White - anticipated maximum 80%
 - Native Hawaiian/Other Pacific Islander
 - Asian
 - Subject refused
- Ethnicity
 - Hispanic/Latino
 - Non-Hispanic/Non-Latino
 - Subject refused
- Diabetes cohorts based on BMI percentile:

Weight Status Category	Percentile Range	N=Minimum
Underweight	Less than the 5th percentile	2
Healthy weight	5th percentile to less than the 85th percentile	30
Overweight	85th to less than the 95th percentile	4
Obese	Equal to or greater than the 95th percentile	1

BMI Percentiles according to CDC:

http://www.cdc.gov/healthyweight/assessing/bmi/childrens_bmi/about_childrens_bmi.html

- Gender
 - Male (minimum N=80)
 - Female (minimum N=80)
- Hypoglycemic awareness
 - Patients with intact hypoglycemic awareness (minimum N=60)
 - Patients who have impaired hypoglycemic awareness (minimum N=40)

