10.1 Visit 1 - Day 0: Consent and Screening

General

Eligibility:

This study is open to all individuals who meet the eligibility criteria. Subjects will be considered enrolled after they have signed the Informed Consent form. The Investigational Center will be responsible for making adequate source documentation available to the sponsor to verify subject eligibility.

General

Standard Care:

It is expected that subjects will continue to undergo their routine diabetes care as per clinic standard. During routine quarterly visits data collection for the study will be obtained by the designated staff.

General

Investigational Center staff will:

- Obtain informed consent/Accent from subject/parent/caregiver
 - Subjects 7-15 years should provide assent in addition to Informed Consent from parent/caregiver
- Assess eligibility of subjects to participate in the study
- Collect demographic information and baseline characteristics, including age, gender, race, ethnicity and medical diagnosis, duration of diabetes (Screening eCRF).
- Record concomitant medications on appropriate CRF
- Obtain blood sample(s) to complete required screening A1C test, if all eligibility criteria (excluding those involving blood test results) are met:
Note: All collected blood specimens will be sent to and tested by a NGSP certified Central Laboratory. A1C testing must follow National Glycohemoglobin Standardization Program (NGSP) standards. This A1C will be used for data analysis.
- Obtain blood samples to complete required screening tests, i.e. TSH (also T3, T4 if TSH is abnormal), Creatinine
- Perform screening labs including urine or serum pregnancy test
- Subjects may be rescreened up to a maximum of two times if they do not meet inclusion/exclusion criteria at the time of their original screening
- Register subjects in CareLink Clinical (see Investigator/Coordinator binder for details) and **upload insulin pump**
- Disburse devices and supplies (e.g., pump, transmitter, glucose sensors, Bayer meter, meter strips, ketone strips) to each study subject
- Administer the following questionnaires:
 - Hypoglycemia awareness questionnaire
 - Score of 4 or more is impaired awareness. It means that subjects with this score will be assigned to the impaired hypoglycemic awareness cohort.
 - Score of 3 or less is aware. It means that subjects with this score will be assigned to the intact hypoglycemic awareness cohort.
 - EQ-5D Youth
 - Hypoglycemia Fear Scale (HFS) – Child/Teen

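### The multiple-imputation check on the completers-only test covers everyone who signed consent, so up to 100 of 140 imputed children could be ineligible, with an effect that depends on an imputation model not visible in the SAP

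*SAP*

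**What the plan says.** SAP 3.1.2.2 runs the primary analysis on subjects who complete the trial and adds one check: "Sensitivity analysis will be performed in the ITT population with multiple imputations". The same section defines the set: "The Intention to Treat (ITT) population will include all enrolled subjects". Protocol 10.1 fixes what enrolled means: "Subjects will be considered enrolled after they have signed the Informed Consent form". Protocol 5.1 gives the numbers: "Up to 300 subjects will be enrolled so that there will be 200 subjects who are eligible to participate in the study". SAP 3.1.1 and 3.1.2.1.2 repeat them.

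Under Protocol 10.1, the Visit 1 A1C sample is taken only once the criteria that need no blood result are met. A child who fails one of those may therefore be enrolled without any A1C. The section also allows a child to be rescreened up to twice.

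The visible text gives no imputation model, no missing-data assumption, no rule for a child without a baseline A1C and no exclusion of screen failures. SAP 3.1.5.1 is followed by redacted blocks, and the next visible heading is 3.1.5.4.

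**The concern.** A completers-only primary analysis needs a check on one question: would the answer change if the children who started the system and left were counted? The check should therefore contain the children who started the system. Read together, the definitions add children who failed screening. They have no A1C after baseline, and some may have none at all. Their 12-month values would be produced wholly by the model, so they bring no evidence on dropout or on Threshold Suspend use.

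At stake is how the check can be read. If most imputed values belong to ineligible children, agreement with the completer result may owe something to who failed screening, and so may disagreement. The primary decision, an upper confidence limit compared with 0.4%, is not affected.

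**Working it through.** **1. The plan's own figures.** The inputs in SAP 3.1.2.1.1 are a margin of 0.4, one-sided alpha of 0.025, an SD of change of 1 and a true change of nil ("Assuming the mean of change in A1C from baseline to the 12-month follow-up visit is zero"). For 100 completers, power = Φ(0.4 × √100 / 1 − 1.96) = Φ(2.04) = 97.9% (97.7% by noncentral t). This agrees with "a total of 100 subjects will provide over 95% power to detect the non-inferiority". Recruitment in SAP 3.1.2.1.2 is 100 / (0.80 × 0.65) = 192.3, rounded up to 193. Both reproduce.

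**2. Who is imputed.** At the ceiling, 300 − 200 = 100 enrolled children are ineligible.

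- At 20% dropout among 200 there are 160 completers and 40 dropouts. Imputed: 40 + 100 = 140 of 300 (46.7%). Ineligible share of the imputed: 100/140 = 71%. With the 200 eligible only: 40/200 = 20% imputed.
- At the 9.3% that the SAP cites there are 18.6 expected dropouts. Imputed: 118.6 of 300 (39.5%). Ineligible share: 100/118.6 = 84%.

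**3. Effect on the estimate when screen failures resemble treated children at baseline.** The simulations used 400 trials with 20 imputations each. Their settings are assumptions, not document figures.

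- *Sequential imputation over all visits.* Scenario: 160 completers with mean change 0, and 40 dropouts rising 1.0 point by month 12 but seen only to month 6. Three separate runs gave estimates of 0.097 to 0.102 without screen failures and 0.098 to 0.107 with 100. In one run the standard error was 0.070 against 0.071, in another 0.077 against 0.078. In a second scenario, dropout depended on the 6-month change and the completer mean was −0.16; the estimate was 0.00 with 200 children and 0.00 with 300. There is no dilution in either scenario.
- *Screen failures filled from completers, dropouts carrying their own excess.* With excess e, the shift from the completer mean is e × 40/200 in the eligible set and e × 40/300 in the enrolled set. For e = 0.5, 1.0 and 1.5 that is 0.10, 0.20 and 0.30 against 0.067, 0.133 and 0.200. The fraction lost is 100/300, one third; with 30 screen failures it would be 30/230 = 13%. When 12-month A1C was imputed from completers given whatever each child had, 0.102 fell to 0.069, a loss of 0.033/0.102 = 32%. A further run lost between a quarter and a third.
- *Imputation from baseline alone for everyone.* In the second scenario the estimate stayed at the completer value of −0.16 with 200 or 300 children. Here the model hides the dropouts, whichever set is used.

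**4. Effect when screen failures differ at baseline.** Let 12-month A1C regress on baseline with slope b, and let the 100 screen failures have a mean baseline that is d above that of treated children. The expected move in the estimate is −(1 − b) × d × 100/300. With assumed b = 0.65 and d = +0.5, it is −0.35 × 0.5/3 = −0.058; with d = −0.5 it is +0.058. Simulation under sequential imputation agreed: 0.08 became 0.02 or 0.14. The documents give neither b nor d.

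**The case against.** The strongest reply is that the set does not matter. Standard imputation over visits fills a screen failure's 3- and 6-month values from all treated children, later dropouts included, so screen failures receive the treated average and not the completer average. This stands for the first model in step 3. It does not stand in general: step 4 shows a shift under the same kind of imputation once there is regression to the mean and a baseline difference.

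Three further points stand. The 100 is a ceiling, and no screen-failure rate is given. Devices are handed out at the same Visit 1 as screening, so a child who later fails on a laboratory result may have received the pump; ineligible is therefore safer than never used the device. And the redacted subsections may hold an imputation model or further sensitivity analyses, so this is the only visible check and not demonstrably the only one.

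A reader might infer more: that the check is necessarily padded toward the completer result, that its standard error is narrower, or that completer means of about 0.12 to 0.17 would pass as written and fail among eligible children. The documents do not support this. Each claim needs a particular model that treats screen failures as completers and dropouts differently, and the visible SAP names none.

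**Conclusion.** The concern holds as a defect in the analysis set. As written, the visible sensitivity analysis imputes 12-month A1C for everyone who signed consent, and at the ceiling with 20% dropout 100 of the 140 imputed children were never eligible. That follows from the documents' own definitions and counts.

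The size of the effect on the estimate is conditional:

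- about none under sequential missing-at-random imputation with similar baselines;
- up to about one third of the dropout signal lost if 12-month values come from completers;
- about 0.06 points in either direction for an assumed slope of 0.65 and a baseline difference of 0.5.

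This is a secondary check, and no visible text makes trial success depend on it. It should still be corrected, because it is the visible safeguard for a completers-only primary analysis.

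**What to change.** In SAP 3.1.2.2, run the multiple-imputation sensitivity analysis on eligible subjects who were dispensed the study pump and have a baseline A1C, each child counted once despite rescreening, with the imputation using all observed A1C visits. If a model already stands in the redacted text, only the set needs changing. Protocol 11.5 notes that some subjects obtained devices commercially under an early protocol version; the wording should say that they count as having received the pump.

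The safety population is also defined as all enrolled. That is a separate question, and this change leaves it alone.

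The cost is a sentence or two in the SAP, with no new data and no extra patients. The sensitivity set becomes smaller, and its result may look slightly less favourable.
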